9.2.4.1 Adverse events

-

9.2.4.2 Laboratory parameters

-

9.2.4.3 Vital signs

-

SUPSI

9.2.5 Assessments in participants who prematurely stop the study

There is no disadvantage for the participants if they (arbitrarily) discontinue study participation, and no further interventions are necessary for follow-up treatment.

However, if participation in the study is cancelled due to an injury sustained during participation, this will be recorded and reported to the sponsor, the head of the research laboratory, the study director, and the supervisor of the study. The report is also sent to Thim van der Laan AG's public liability insurance to ensure the appropriate follow-up treatment.

The following are recorded:

- Date and time of the incident
- Course of the incident
- Persons involved & witnesses
- Study ID (issued by the CEC)
- Personal details of the person concerned (if not previously recorded)

9.3 Procedures at each visit

9.3.1 Single measurement

The project involves multiple visits.

9.3.2 Multiple visits

The project involves multiple visits with a maximum duration of 255 minutes, which are organised as follows:

1. Subject information & informed consent

The test subjects are given comprehensive information about the procedure and possible risks before agreeing to participate in the study. They also receive the information in written form and have the opportunity to ask questions. The informed consent form explains to them what their rights and obligations are when participating and that they may withdraw from participation at any time without giving reasons and without incurring any disadvantages. More detailed information can be found in section 2.7.

2. Preparing the test subjects

If the test subject is willing to participate, she is instructed to get changed in a separate room.

First, the locations for the placement of the electrodes are marked with a skin-friendly pen (eyeliner) and, if necessary, individual locations of the EMG electrode placements are shaved (both were explained to the test subject beforehand according to a checklist). The electrodes are then attached. The electrodes are attached to the lower third of the anterior thigh muscle. Furthermore, the locations for placing the sensors for measuring skin temperature and oxygen saturation on the thigh are marked with a skin-friendly pencil (eyeliner). A heart rate monitor is applied to the test subject and to start the measurement of the core body temperature, the test subject is asked to take a capsule. It is also checked that no metal jewellery is worn on the body before the test subjects complete the jump protocol.

3. Measurements

The tests are carried out, and the data is collected in accordance with the test protocol.

4. Compensation and Conclusion

After completion of the individual measurement, the test subject is asked to change again in a separate room. Afterwards, she is asked how she feels. The subject is asked to report back to the laboratory at intervals of 24 hours, 48 hours and 72 hours to carry out the follow-up measurements. MVIC, the

SUPSI

maximum jump height, skin temperature, core body temperature, heart rate, inflammation parameters, muscle swelling and oxygen saturation in the thigh are measured again. Furthermore, subjective muscle soreness and general exhaustion are recorded. After completion of the measurements, the test subject receives the compensation to which they are entitled in accordance with the information in the advertisement:

Flat rate CHF 50 after completion of the measurements (measurement time: after 72 hours).

SUPSI

10. REGULATORY ASPECTS AND SAFETY

Other clinical trial with a medical device in the risk category Cat. A (chap. 4)

No medication is administered to the test subjects and no tissue samples are taken. Only minimally invasive methods are used.

The current regulations of the Canton of Graubünden and those of the FOPH for protection against the coronavirus will be taken into account and implemented when conducting the study.

10.1 Local regulations / Declaration of Helsinki

This study is conducted in compliance with the protocol, the current version of the Declaration of Helsinki, the ICH-GCP, the HRA as well as other locally relevant legal and regulatory requirements.

10.2 (Serious) Adverse Events and notification of safety and protective measures

An Adverse Event (AE) is any untoward medical occurrence in a patient or a clinical investigation subject, which does not necessarily have a causal relationship with the trial procedure. An AE can therefore be any unfavourable or unintended finding, symptom, or disease temporally associated with a trial procedure, whether or not related to it.

A Serious Adverse Event (SAE) (ClinO, Art. 63) is any untoward medical occurrence that

- Results in death or is life-threatening,
- Requires in-patient hospitalisation or prolongation of existing hospitalisation,
- Results in persistent or significant disability or incapacity, or
- Causes a congenital anomaly or birth defect

Both Investigator and Sponsor-Investigator make a causality assessment of the event to the trial intervention, (see table below based on the terms given in ICH E2A guidelines). Any event assessed as possibly, probably or definitely related is classified as related to the trial intervention.

Relationship	Description
Definitely	Temporal relationship Improvement after dechallenge* Recurrence after rechallenge (or other proof of drug cause)
Probably	Temporal relationship Improvement after dechallenge No other cause evident
Possibly	Temporal relationship Other cause possible
Unlikely	Any assessable reaction that does not fulfil the above conditions
Not related	Causal relationship can be ruled out

*Improvement after dechallenge only taken into consideration, if applicable to reaction

SUPSI

Both Investigator and Sponsor-Investigator make a severity assessment of the event as mild, moderate or severe. Mild means the complication is tolerable, moderate means it interferes with daily activities and severe means it renders daily activities impossible.

Reporting of SAEs (see ClinO, Art. 63)

All SAEs are documented and reported immediately (within a maximum of 24 hours) to the Sponsor-Investigator of the study.

If it cannot be excluded that the SAE occurring in Switzerland is attributable to the intervention under investigation, the Investigator reports it to the Ethics Committee via BASEC within 15 days.

Notification of safety and protective measures (see ClinO, Art 62, b)

If immediate safety and protective measures have to be taken during the conduct of the study, the investigator notifies the Ethics committee of these measures, and of the circumstances necessitating them, within 7 days.

10.3 (Periodic) safety reporting

An annual safety report (ASR/DSUR) is submitted once a year to the local Ethics Committee by the Investigator (ClinO, Art. 43 para).

10.4 Amendments

Substantial changes to the study setup and study organization, the protocol and relevant study documents are submitted to the Ethics Committee for approval before implementation. Under emergency circumstances, deviations from the protocol to protect the rights, safety and well-being of human subjects may proceed without prior approval of the Ethics Committee. Such deviations shall be documented and reported to the Ethics Committee as soon as possible.

A list of all non-substantial amendments will be submitted once a year to the competent EC together with the ASR.

10.5 (Premature) termination of study

The Sponsor-Investigator may terminate the study prematurely according to certain circumstances, e.g.

- Ethical concerns,
- Insufficient participant recruitment,
- When the safety of the participants is doubtful or at risk (e.g. when the benefit-risk assessment is no longer positive),
- Alterations in accepted clinical practice that make the continuation of the study unwise, or
- Early evidence of harm or benefit of the experimental intervention

Upon regular study termination, the Ethics Committee is notified via BASEC within 90 days (ClinO, Art. 38).

Upon premature study termination or study interruption, the Ethics Committee is notified via BASEC within 15 days (ClinO, Art. 38).

SUPSI

10.6 Insurance

The notification is also sent to the business liability insurance (Basler Versicherung) of Thim van der Laan AG in Landquart. Proof of this insurance policy will also be submitted.

SUPSI

11. STATISTICAL METHODS

11.1 Hypothesis

Jump height (cm)

H0 The jump height is not increased by the hot water immersion compared to the cold water immersion, hypoxia group and passive control group during a 72-hour recovery phase.

H1 The jump height is increased by the hot water immersion compared to the cold water immersion, hypoxia group and passive control group during 72 hours.

MVIC (kg)

H0 MVIC performance is not increased by hot water immersion compared to cold water immersion, hypoxia group, and passive control group during a 72-hour recovery period.

H1 The MVIC efficiency is increased by hot water immersion compared to cold water immersion, hypoxia group and passive control group during 72 hours.

Muscle swelling (mm)

H0 Muscle swelling is not increased by hot water immersion compared to cold water immersion, hypoxia group, and passive control group during a 72-hour recovery period.

H1 Muscle swelling is increased by hot water immersion compared to cold water immersion, hypoxia group and passive control group for 72 hours.

Blood oxygen saturation (%)

H0 Blood oxygen saturation is not increased by hot water immersion compared to cold water immersion, hypoxia group and passive control group during a 72-hour recovery period.

H1 The oxygen saturation of the blood is increased by the hot water immersion compared to the cold water immersion, hypoxia group and passive control group during 72 hours.

Oxygen Saturation Muscle (%)

H0 Oxygen saturation of the thigh muscle is not increased by hot water immersion compared to cold water immersion, hypoxia group and passive control group during a 72-hour recovery period.

H1 The oxygen saturation of the thigh muscle is increased by hot water immersion compared to cold water immersion, hypoxia group and passive control group during 72 hours.

Heart rate (b/min)

H0 The heart rate is not increased by the hot water immersion compared to the cold water immersion, hypoxia group and passive control group during a 72-hours of recovery.

H1 Heart rate is increased by hot water immersion compared to cold water immersion, hypoxia group and passive control group during 72 hours.

SUPSI

Skin temperature (°C)

H0 Skin temperature is not increased by hot water immersion compared to cold water immersion, hypoxia group and passive control group during a 72-hour recovery period.

H1 Skin temperature is increased by hot water immersion compared to cold water immersion, hypoxia group and passive control group during 72 hours.

Core Body Temperature (°C)

H0 Core body temperature is not increased by hot water immersion compared to cold water immersion, hypoxia group, and passive control group during a 72-hour recovery period.

H1 Core body temperature is increased by hot water immersion compared to cold water immersion, hypoxia group and passive control group during 72 hours.

Inflammation parameters (CRP, IL6, CK)

H0 Inflammation levels are not increased by hot water immersion compared to cold water immersion, hypoxia group, and passive control group during a 72-hour recovery period.

H1 The inflammation rates are increased by hot water immersion compared to cold water immersion, hypoxia group and passive control group during 72 hours.

Subjective information on shortness of breath (mod. BORG)

H0 Subjective information on shortness of breath is not increased by hot water immersion compared to cold water immersion, hypoxia group and passive control group during a 72-hour recovery period.

H1 The subjective information on shortness of breath is increased by hot water immersion compared to cold water immersion, hypoxia group and passive control group during 72 hours.

Subjective data on general exhaustion (BORG)

H0 The subjective data on general fatigue are not increased by the hot water immersion compared to the cold water immersion, hypoxia group and passive control group during a 72-hour recovery period.

H1 The subjective data on general fatigue are increased by the hot water immersion compared to the cold water immersion, hypoxia group and passive control group during 72 hours.

Subjective muscle soreness (VAS)

H0 Subjective muscle soreness is not increased by hot water immersion compared to cold water immersion, hypoxia group, and passive control group during a 72-hour recovery period.

H1 Subjective muscle soreness is increased by hot water immersion compared to cold water immersion, hypoxia group and passive control group during 72 hours.

SUPSI

Thermal comfort and temperature perception

H0 Thermal comfort and temperature perception are not increased by hot water immersion compared to cold water immersion, hypoxia group and passive control group during a 72-hour recovery period.

H1 Thermal comfort and temperature perception are increased by hot water immersion compared to cold water immersion, hypoxia group and passive control group during 72 hours.

A 2-factor analysis is carried out.

Factor 1: Intervention (cold water immersion vs. hot water immersion vs. hypoxia group vs. Passive Control Intervention)

Factor 2: Time (Baseline, 0, 24 hours, 48 hours, 72 hours)

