4.2 Primary Objective

In this project, the effect of post-activity cooling or warming on physiological and psychological recovery parameters is measured and compared to the hypoxia intervention and the passive control group.

Physiological measurements

- Jump height measurement (cm)
- Maximum voluntary isometric thigh contraction (kg)
- Muscle swelling (mm)
- Blood oxygen saturation (%)
- Oxygen saturation of the muscles (%)
- Heart rate (bpm)
- Skin temperature (°C)
- Core Body Temperature (°C)
- Inflammation parameters; IL6 (pg/ml), CRP (mg/dl), creatine kinase (U/L)

Psychological measurements

- Dyspnea questionnaire (mod. Borg scale)
- Exhaustion questionnaire (Borg scale)
- Subjective muscle soreness (VAS scale)
- Thermal comfort and thermal sensation

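### All 13 hypothesis pairs in section 11.1 predict an increase under hot water and none tests cold water, so they match neither the objective, the synopsis contrasts nor the non-directional test

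*Combined protocol and SAP*

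**What the plan says.** Section 11.1 lists one H0/H1 pair per outcome, with CRP, IL6 and CK sharing one pair. The wording is the same throughout. For jump height the alternative is "The jump height is increased by the hot water immersion compared to the cold water immersion, hypoxia group and passive control group during 72 hours". For soreness, H0 begins "Subjective muscle soreness is not increased by hot water immersion compared to cold water immersion" and H1 is "Subjective muscle soreness is increased by hot water immersion compared to cold water immersion, hypoxia group and passive control group during 72 hours". For swelling, H0 begins "Muscle swelling is not increased by hot water immersion compared to cold water immersion" and H1 is "Muscle swelling is increased by hot water immersion compared to cold water immersion, hypoxia group and passive control group for 72 hours". For the blood markers H1 begins "The inflammation rates are increased by hot water immersion".

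The primary objective in section 4.2 is wider: "the effect of post-activity cooling or warming on physiological and psychological recovery parameters is measured", with the hypoxia and passive control arms as comparators. The synopsis, under Statistical Considerations, lists five pairwise contrasts, including cold water against control and hot water against control.

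Sections 11.1 and 11.4.2 plan a two-factor repeated measures analysis (labelled MANOVA) with all four arms as levels of the intervention factor and five time points, at the 5% level. Sidedness is not stated and 11.4.2 names no pairwise contrasts.

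**The concern.** A null hypothesis of no increase contains every result from no effect to a large reduction. Where a higher value means worse recovery, the result that would favour hot water is therefore part of H0, and the alternative describes only harm. Cold water appears in the pairs only as a comparator for hot water, so its own effect against control has no formal hypothesis.

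The trial is meant to support recommendations on thermotherapy (section 3.1, aim of the study). If a significant result showed less soreness under hot water, the team would have two choices. It could follow 11.1 literally and conclude nothing in favour of hot water, or it could set the written hypothesis aside once the data are known. The second course is the sensible one scientifically, but it leaves the direction of success to be settled after the results are seen.

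**Working it through.** The plan gives no figure on this point to reproduce, and the sample size calculation does not bear on it. The check is a count and a comparison of sections.

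**Step 1. Count and direction.** The pairs in 11.1 cover jump height, MVIC, muscle swelling, blood oxygen saturation, muscle oxygen saturation, heart rate, skin temperature, core temperature, inflammation parameters, shortness of breath, exhaustion, soreness, and thermal comfort with temperature perception. That is 13. Alternatives worded as an increase under hot water: 13 of 13.

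**Step 2. What an increase would mean for recovery.**

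| Outcome pairs | Meaning of an increase | Number |
|---|---|---|
| Jump height, MVIC | Better | 2 |
| Soreness, swelling | Worse; clear from the VAS anchors (section 5.1) and the rationale in 3.3 | 2 |
| Exhaustion | Worse, but timing conflicts: 5.1 and 9.2.1 place it only before the intervention, while 9.1 and 9.3.2 also place it at follow-up | 1 |
| Inflammation parameters | Usually worse; arguable for CK, because 3.1 reports a hypothesis that hot water promotes protein release from muscle and so helps maintain function | 1 |
| Shortness of breath | Worse, but 9.1 schedules the modified Borg scale only after the jumps, and 5.1 and 9.2.1 only before the intervention, so on that schedule the baths cannot change it | 1 |
| Thermal comfort and perception | Ambiguous: more comfort in words, but a higher comfort score is less pleasant (5.1) | 1 |
| Blood and muscle oxygen saturation, heart rate, skin and core temperature | The documents do not say which direction is better recovery | 5 |

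Check: 2 + 2 + 1 + 1 + 1 + 1 + 5 = 13. Soreness and swelling are the secure examples of a benefit falling under H0.

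**Step 3. Swelling against the rationale.** Section 3.3 justifies repeating the cold and hot baths after two hours by a possible reduction in the intracellular volume increase after exercise. The swelling alternative in 11.1 predicts more swelling under hot water, which is the opposite direction.

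**Step 4. Arms compared.** Four arms give 4 × 3 / 2 = 6 pairwise comparisons.

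| Comparison | Synopsis contrast | Hypothesis in 11.1 |
|---|---|---|
| Hot vs cold | Yes | Yes |
| Hot vs control | Yes | Yes |
| Hot vs hypoxia | Yes | Yes |
| Cold vs control | Yes | No |
| Cold vs hypoxia | Yes | No |
| Hypoxia vs control | No | No |

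The synopsis names 5 of 6 and section 11.1 covers 3 of 6. The two that the synopsis names and 11.1 omits are the comparisons of cold water with the two arms that section 4.2 sets as comparators.

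**Step 5. Hypotheses against the test.** An F test from a two-factor repeated measures model asks whether the arms differ, or whether their courses over time differ, in any direction. Its null is equality, whereas the null in 11.1 is equality or reduction. The test and the written hypotheses therefore do not correspond.

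**The case against.** The strongest reply is that the analysis does not depend on this wording. The planned model contains all four arms and its F test has no direction, so less soreness under hot water, or a difference between cold water and control, can still come out as significant. The synopsis already names cold against control and hot against control. All of this stands, and it limits the point to the hypotheses themselves.

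The direction may also be partly deliberate. Section 3.1 reports more recent studies in which cold water was more effective than hot, so predicting more soreness under hot than under cold water is coherent. That does not explain predicting more soreness under hot water than under passive control, or more swelling against the rationale in 3.3.

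Four stronger readings are tempting, and the documents do not support them:

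- A reader might infer that the trial has almost no chance of showing a benefit on soreness. That would hold for a one-sided test for an increase, and no such test is planned.
- A reader might infer that cold water will not be compared with control. The synopsis lists that contrast and the model includes both arms.
- A reader might infer that a significant reduction would have to be reported as a failure to reject H0. No section sets such a decision or reporting rule; it follows only from a literal reading of 11.1.
- A reader might count every symptom and blood outcome as one where the stated direction is harm. Breathlessness, CK and thermal comfort do not bear that out, and exhaustion is uncertain because of its timing.

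**Conclusion.** Section 11.1 is wrong as written. All 13 alternatives are increases under hot water. For at least two outcomes, soreness and swelling, a recovery benefit of hot water lies inside H0, and for swelling the alternative contradicts the protocol's own rationale. None of the 13 pairs takes cold water as the tested arm, so 2 of the 5 synopsis contrasts have no hypothesis. The hypotheses match neither the objective in 4.2, nor the synopsis contrasts, nor the test in 11.4.2.

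The consequence is for what can formally be concluded, not for what can be detected: the data collected and the planned model are unaffected. The conclusion rests on reading 11.1 literally and on higher soreness and swelling being worse recovery. It needs no assumption about effect size, arm size or allocation.

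**What to change.** Before the data are analysed:

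1. Rewrite each pair in 11.1 as two-sided. H0: the arms do not differ in the course of the outcome over time. H1: they do. This corresponds to the intervention and time factors already planned.
2. Carry the five synopsis contrasts, including cold water against control and hot water against control, into both 11.1 and 11.4.2. State whether hypoxia against control is of interest, since it appears in neither place.
3. State for each outcome which direction means better recovery, or that none is defined. For thermal comfort, say whether an increase refers to the score or to the sensation.
4. State in 11.4.2 that the 5% level is two-sided for the pairwise contrasts.

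The cost is rewording of 11.1 and a few lines in 11.4.2, with whatever ethics committee notification an amendment requires. No new data, design change or different model is needed.

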11.2 Determination of Sample Size

Based on a study with a comparable setting (Ferreira-Junior et al. 2014, Fonda et al. 2013, Hausswirth et al. 2011) and outcome, the power analysis was calculated using the G*Power App (Düsseldorf, North Rhine-Westphalia, DEU), whereby a minimum number of 33 subjects was considered necessary to ensure the statistical power (0.80) to detect a parameter difference at the 5% significance level. Taking into account a possible loss of 20% of the data sets (due to drop-out or incomplete data sets), the minimum sample size is 40 participants. The following figure shows the G-Power calculation that was used to determine the sample size.

[figure not shown]

Figure: Sample Size Calculation

SUPSI

